14.2.3.3. Stopping Rule for Excessive Toxicity

We will use a Bayesian monitoring scheme to continuously monitor the dose limiting toxicity rate of the study combination at 30%. The DLT is defined generally as grade 3 and 4 toxicity, see section 8.1 for more detailed definitions. Again, a non-informative prior of Beta (0.5, 0.5) for the DLT rate will be used. We will hold patient recruitment if the posterior probability $\text{Pr}(\text{SAE rate} > 30\%) \leq 0.7$, and the study committee and the PI will then decide whether to modify or discontinue the study. The stopping boundary for toxicity is given in the following table:

Number of SAEs \geq	in Number of Patients =
2	3-5
3	6-7
4	8-10
5	11-13
6	14-16
7	17-19
8	20-22
9	23-26
10	27-29
11	30

We simulate the operating characteristics under various assumed true toxicity rates (see the following table):

Scenario	Prob.Of.Tox	Prob.Early.Stop
1	0.1	0.0885
2	0.2	0.3332
3	0.3	0.6727
4	0.4	0.9128

14.2.3.4. Analysis of Safety (for both the phase I portion and the phase II portion)

We will consider a toxicity event to be an adverse event (evaluated by CTCAE 5.0) that is possibly, probably, or definitely related to treatment. Toxicity will be considered attributable to both study drugs, unless investigator determines one of the drugs is a more likely culprit (e.g. CMV due duvelisib). The maximum grade of toxicity for each category of interest will be recorded for each patient and the summary results will be tabulated by category and grade. These will also be done for early toxicities (within 4 weeks) and late toxicities (after 4 weeks) separately.

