3.2.2 Secondary Endpoints

Several secondary endpoints will be analyzed as follows:

- Acute and late toxicities rates throughout treatment, as graded by CTCAE v5.0 in patients at each dosing interval and in the expansion cohort
- Clinical benefit of combination therapy, defined as complete response, partial response and stable disease as assessed by RECIST v1.1, initially assessed at 12 weeks after initiation of therapy and subsequently at 12-week intervals until progression

- Duration of response defined by time at which measurement criteria are first met for complete response or partial response until the first time at which progressive disease is objectively documented
- Progression-free survival defined as time at start of treatment and first date of documented progression or death due to any cause
- Overall Survival defined as the time of start of treatment and the date of death due to any cause. Patients who are alive will be censored at the time of the last follow-up. Patients will be followed for survival for 5 years.
- Safety of the combination of anti-PD1 and duvelisib measured by adverse events graded by CTCAE v5.0. Adverse events will be captured during treatment and 100 days after discontinuing treatment. We will continuously monitor for DLTs as defined in section 8.1 that are possibly, probably or definitely related to treatment. If the adverse event rate exceeds acceptable limits, the study will be modified or discontinued.
- Subset analysis will be performed to determine how certain disease characteristics affect response to the combination, including prior time prior to progression while on anti-PD1 therapy, presence of CNS disease, radiated CNS disease and tumor BRAF mutation status.

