8.1 Dose Limiting Toxicities

Acute dose limiting toxicities (DLTs) are defined as any of the following AEs and laboratory abnormalities considered possibly, probably, or definitely related to study treatment that occur any time from the initial dose of duvelisib in combination with nivolumab through day 28 of treatment. Toxicities occurring from day 29 through 28 days after completion of treatment will be considered late toxicities. Only acute DLTs will be considered for decisions to continue enrollment at the current dose level or proceed to the next dose level. Acute and late toxicities will be considered when deciding on the RP2D and will be discussed in monthly Data Safety Monitoring Board (DSMB) meetings. See Section 15.0 for further details.

Severity of adverse events will be graded by National Cancer Institute Common Terminology Criteria for Adverse Events version 5.0 (CTCAE v5.0). A goal of $\leq 33\%$ DLTs at each dose level will be considered acceptable.

Whenever possible, biopsies are recommended if they can be done safely to help determine between immune-related and other etiologies of toxicity, particularly for rash and colitis. Biopsies for elevated liver enzymes and/or for pneumonitis should be considered if deemed feasible and safe in the context of risk:benefit evaluation. General criteria for consideration of biopsy:

- Diarrhea/colitis
 - Biopsy proven grade ≥ 3 immune-related colitis
 - Diarrhea of grade ≥ 3 that does not respond to treatment with steroids within 5 days
- Pneumonitis
 - Immune-related pneumonitis grade ≥ 2

- Any grade ≥ 3 pneumonitis
- Hematologic abnormalities
 - Neutropenia grade 4 despite holding duvelisib for 7 days
 - Thrombocytopenia grade ≥ 3 with bleeding
 - Thrombocytopenia grade 4
- Other immune-related toxicities
 - Any grade ≥ 3 toxicity that does not respond to treatment within 5d
- For the remainder of non-hematologic toxicities, grade ≥ 3

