11.1 Infections

Duvelisib carries a black box warning regarding infection risk, most often URI and pneumonia. The median time to infection was 3 months, with the majority occurring prior to 6 months. For any grade 3 or higher infection, duvelisib must be held. For patients with suspected PJP, duvelisib should be held and permanently discontinued if PJP is confirmed. PJP prophylaxis is required for all patients and should continue until CD4+ T cell count is > 200 cells/ μ L or for 14 days after last dose of duvelisib. For patients with CMV reactivation or infection, drug should be held until resolved. If resumed, patients should be monitored at least monthly for reactivation and prophylaxis should be considered. For other infections, recommended dose reductions are listed in Table 7.5.

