11.2 Diarrhea/Colitis

Diarrhea and colitis were also seen frequently. Median time to onset was 4 months, with the majority of cases occurring before 8 months, and symptoms could be prolonged (median duration 0.5 months). For grade 1-2 diarrhea or asymptomatic colitis, initiate supportive care with antidiarrheal agents, continue medication and monitor weekly until resolution. If unresponsive to antidiarrheals then duvelisib should be held and enteric steroids such as budesonide should be started. Duvelisib may then be restarted at a reduced dose as deemed clinically appropriate by the treating physician.

For subjects with abdominal pain, stools with mucus or blood, or severe diarrhea, hold duvelisib and start systemic or enteric steroids. If possible, a colonoscopy and work-up for immune-mediated colitis should be performed. Restart duvelisib at a reduced dose upon resolution of symptoms to less than or equal to CTCAE Grade 1. For recurrent events, duvelisib should be permanently discontinued.

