11.4 Pneumonitis

Serious cases of pneumonitis occurred with duvelisib. Median time to onset of any grade was 4 months with the majority of cases occurring prior to 9 months and with a mean duration of event of 1 month. Subjects should report new cough or shortness of breath. Patients who have pulmonary signs and symptoms such as cough, dyspnea, hypoxia, radiologic changes, or decline of >5% in oxygen saturation should have duvelisib held and be evaluated. Infectious etiologies should be treated as above. Systemic steroids should be considered. For moderate disease, reduced duvelisib doses can be considered. If non-infectious pneumonitis recurs or does not respond to steroid therapy, discontinue duvelisib. For severe or life-threatening pulmonary disease, duvelisib should be permanently discontinued.

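### The phase II toxicity stopping rule, on its most coherent reading, counts only events to day 28, although the protocol's own median onsets for four duvelisib toxicity classes are 3 to 4 months

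*Combined protocol and SAP*

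**What the plan says.** - **Monitored event.** Section 14.2.3.3 states: "We will use a Bayesian monitoring scheme to continuously monitor the dose limiting toxicity rate of the study combination at 30" per cent. It puts the Beta(0.5, 0.5) prior on the DLT rate and adds: "The DLT is defined generally as grade 3 and 4 toxicity, see section 8.1 for more detailed definitions". Section 3.2.2 makes the same link: "We will continuously monitor for DLTs as defined in section 8.1".
- **Window.** Section 8.1 counts related events "from the initial dose of duvelisib in combination with nivolumab through day 28 of treatment" and classes anything from day 29 as late toxicity. The follow-up part of Section 4.4 also gives 28 days for DLT evaluation. No separate window is stated for phase II.
- **Competing labels.** The posterior statement and the boundary table in 14.2.3.3 refer to SAEs, and the synopsis to the severe adverse event rate.
- **Onset, from earlier duvelisib experience.** Infection: "The median time to infection was 3 months, with the majority occurring prior to 6 months". Diarrhea/colitis: "Median time to onset was 4 months, with the majority of cases occurring before 8 months". Pneumonitis: "Median time to onset of any grade was 4 months with the majority of cases occurring prior to 9 months". Section 11.3 gives a 3-month median for cutaneous reactions. Treatment may last 12 months (Section 4.4.1).
- **Late toxicity.** It is tabulated separately (14.2.3.4) and discussed at monthly DSMB meetings (8.1, 14.1.1). The DSMB and DSMC may suspend accrual (10.1). No numerical limit is attached to it.

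**The concern.** A first-cycle window is conventional for dose escalation, where cohort decisions have to be made quickly. Carried into phase II, it settles which toxicities the formal rule can see. Monitoring continuously says how often the rule is checked. It does not say how long each patient can contribute an event.

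If counting stops at day 28, a patient with severe colitis at month 4 enters the boundary as a patient without an event. The operating-characteristics table would then reassure readers about a rate that leaves out most events in four of the toxicity classes for which Section 11 gives specific guidance. Recruitment could continue at a high on-treatment toxicity rate without the boundary being reached, leaving late toxicity to discretionary review alone.

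**Working it through.** **1. Reproduce the plan's figures.** Inputs from 14.2.3.3: prior Beta(0.5, 0.5), reference rate 30%, cut-off 0.7, 30 patients. The boundary at n patients is the smallest r with 1 − BetaCDF(0.30; 0.5 + r, 0.5 + n − r) > 0.7. For example:
- n = 3: r = 2 gives 0.911 and r = 1 gives 0.584, so the boundary is 2.
- n = 30: r = 11 gives 0.790 and r = 10 gives 0.663, so the boundary is 11.

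This matches the table at every n from 3 to 30. It needs the inequality to be > 0.7; the hold condition is printed as ≤ 0.7, a separate slip. An exact binomial recursion with a look after each patient from 3 to 30 gives stopping probabilities of 0.0885, 0.3332, 0.6727 and 0.9128 at rates of 0.1, 0.2, 0.3 and 0.4, identical to the plan. The arithmetic is sound; the open question is which rate it describes.

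**2. Share of events inside 28 days.** Every quoted median lies beyond day 28, so less than half of onsets in these classes fall in the window, whatever the shape of the curve. For a specific share, assume Weibull onset with median m months and shape k: F(t) = 1 − 2^(−(t/(30.44m))^k). With k = 1 (exponential), F(28) = 0.191 for m = 3 and 0.147 for m = 4.

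**3. Stopping probability at a true 40% on-treatment rate.** Counted rate = 0.40 × share, put through the recursion of step 1. Paired values are for 3-month / 4-month medians.

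| Onset assumption | Share by day 28 | Counted rate | P(stop) |
|---|---|---|---|
| All events counted | 100% | 0.400 | 0.913 |
| Ceiling from the medians alone | < 50% | < 0.200 | < 0.333 |
| Front-loaded (k = 0.5) | 31.9% / 28.3% | 0.128 / 0.113 | 0.141 / 0.112 |
| Exponential (k = 1) | 19.1% / 14.7% | 0.077 / 0.059 | 0.053 / 0.032 |
| Delayed (k = 2) | 6.3% / 3.6% | 0.025 / 0.014 | 0.006 / 0.002 |

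At a true 30% rate the stopping probability is 0.673 with all events counted, below 0.192 at the ceiling, and 0.031 / 0.018 under exponential onset.

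**4. Early departure.** Patients stop at progression and the first scheduled scan is at 12 weeks, so some will leave before late events can occur. As an extreme, let everyone leave at day 84. The share is then F(28)/F(84). Exponential: 0.191/0.471 = 40.6% and 0.147/0.380 = 38.8%, giving counted rates of 0.162 / 0.155 and P(stop) of 0.22 / 0.20.

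The ceiling in step 3 presumes that the quoted medians describe on-treatment events in this trial. If onset is front-loaded and everyone also leaves at day 84, the share is 0.319/0.486 = 66% (3-month median) or 0.283/0.438 = 65% (4-month), and P(stop) is 0.55 / 0.53. That exceeds the ceiling but is still well short of 0.91.

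**The case against.** - **The event may not be the 28-day DLT.** The formula and table say SAE and the synopsis says severe adverse event rate. Section 3.2.2 places the monitoring sentence beside adverse-event capture that runs to 100 days after treatment. The day-28 sentence in 8.1 defines acute DLTs and ties them to dose-level decisions, so 14.2.3.3 might be borrowing the event types and not the window. This stands in part. If serious adverse events collected to 100 days after the last dose were meant, the 28-day limit would not apply. But prior and posterior must concern one parameter, the prior is on the DLT rate, and 8.1 is the only definition cited. The DLT reading is the most coherent, and either reading needs the text settled.
- **Late toxicity is already reviewed.** This stands. A reader might infer that late toxicity goes unmonitored, or that 30 patients could be treated with no check. The documents do not support that: monthly review can suspend accrual, and crossing the boundary itself only holds recruitment pending a decision. What is missing is a threshold for late events.
- **The onset figures are imperfect.** This stands. Pneumonitis is stated as any grade and the other three carry no grade, while the rule mainly counts grade 3 or higher. No onset is given for neutropenia, transaminase elevation or the combination. It cannot be said that most of all toxicity falls outside the window, only most of four classes if the medians carry over. Nor should 0.03 to 0.05 stand alone, since it rests on one assumed curve with no early departure.
- **No limit is set for cumulative toxicity.** The 30% here and the 33% in 8.1 are DLT limits. The 40% case shows how the rule behaves; the documents do not call it unacceptable over a year.
- **Late events may arrive too late to act on.** This fails. Enrollment is planned over 18 months, so events at 3 to 4 months can still inform later accrual.

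**Conclusion.** The point holds for the formal rule and its quoted operating characteristics. On the most coherent reading, counting ends at day 28 and more than half of infections, cutaneous reactions, diarrhea/colitis and pneumonitis would not count, provided the protocol's medians apply to this trial. At a true 40% on-treatment rate made up of such events, the chance of stopping falls from 0.91 to below 0.33 without assuming a shape for onset. The specific values between 0.03 and 0.22 depend on the assumed onset curve and time on treatment. The size is therefore uncertain, and the direction is not. The documents do not show a settled decision to ignore late toxicity: they show a phase II event with inconsistent labels and no stated window. This should be corrected before phase II monitoring relies on the rule.

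**What to change.** In Section 14.2.3.3, with matching edits to 3.2.2 and the synopsis:

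1. Replace DLT, SAE and severe adverse event with one defined monitored event.
2. State that, for phase II monitoring, a related toxicity of the 8.1 type counts at any time on treatment, or within a stated window longer than 28 days. Apply this equally to the 6 patients carried over from phase I.
3. Keep the 28-day window for phase I escalation only.
4. Recompute the boundary and operating characteristics for that window and a reference rate suited to it. Say how patients with incomplete follow-up enter the denominator; counting them as event-free biases the posterior downward.

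Recalculation is part of the fix. With the present boundary, exponential onset and a 40% eventual rate, the stopping probability is 0.30 / 0.20 for an 84-day window, 0.67 / 0.53 for 183 days and 0.87 / 0.82 for 365 days (3- / 4-month medians, complete follow-up, no early departure).

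**Cost.** No new data are needed, because adverse events are already collected to 100 days after treatment. The work is a wording change plus a new boundary and simulation. The downside is that the boundary is reached more often unless recalibrated, and each patient's information is complete later.

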Statistical Methodology	For the Phase I study, a modified 3+3 dose finding design is used, with 6 patients at each of 3 dose levels of 15mg daily, 25mg daily and 25mg twice daily. For the Phase II expansion, the expected response rate for treatment of patients with anti-PD1 beyond progression is <14% ² . For this study to be clinically relevant a response rate of at least 20% is sought from the addition of duvelisib. Regimen efficacy will be monitored using a Bayesian method. The trial will be stopped for futility if the posterior probability of response rate is <5% or is >70%. Response rate, progression free survival and overall survival will be analyzed via Kaplan-Meier methods. For safety analyses, a Bayesian monitoring scheme will also be used to monitor the severe adverse event rate.

Safety Evaluations	Patients will be evaluated at clinic visits at least every 2-4 weeks for safety analyses. Blood work will also be tested at these visits to evaluate any adverse effects. For patients with toxicity or other clinical concerns, additional visits and imaging may be warranted at the discretion of the treating physicians and in consultation with a study investigator.
Data and Safety Monitoring Plan	The Data Safety Monitoring Board consists of investigators, regulatory staff, CRS management, clinical research coordinators, data managers and clinic staff, and these will meet regularly at least monthly to discuss trial concerns and study data. The DSMB includes individuals not involved in study design or implementation. Information to be reviewed includes serious adverse events, safety issues, recruitment, accrual, protocol deviations and unanticipated problems. The protocol and investigators will also comply with IRB policy for reporting risk to subjects.

iii. Study Design Schematic

A Phase I/II Study of PI3K γ δ inhibitor Duvelisib in Combination with Nivolumab in Patients with Advanced Unresectable Melanoma who have Progressed on Anti-PD1 Therapy

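### The phase II toxicity hold sentence says the opposite of its own boundary table, and the formula and table header count SAEs where the text monitors DLTs

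*Combined protocol and SAP*

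**What the plan says.** Section 14.2.3.3 sets the phase II toxicity rule. It opens by saying that a Bayesian scheme will "continuously monitor the dose limiting toxicity rate of the study combination at 30" per cent. It refers to section 8.1 for the DLT definition and adds that "a non-informative prior of Beta (0.5, 0.5) for the DLT rate will be used". The operative sentence follows: "We will hold patient recruitment if the posterior probability $\text{Pr}(\text{SAE rate} > 30\%) \leq 0.7", after which the study committee and the investigator decide whether to modify or discontinue the study.

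The boundary table has the column header "Number of SAEs \geq". It runs from 2 events in 3–5 patients to 11 events in 30. A second table is introduced with "We simulate the operating characteristics under various assumed true toxicity rates" and gives early-stop probabilities of 0.0885, 0.3332, 0.6727 and 0.9128 at true rates of 10%, 20%, 30% and 40%.

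Two other places name the monitored event. Section 3.2.2 says "We will continuously monitor for DLTs as defined in section 8.1 that are possibly, probably or definitely related to treatment". The Statistical Methodology row of the Protocol Summary says that "a Bayesian monitoring scheme will also be used to monitor the severe adverse event rate".

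**The concern.** There are two separate faults.

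**Direction.** A toxicity rule should hold recruitment when the posterior probability of excess toxicity is high. As supplied, the sentence holds when that probability is 0.7 or lower, which is when the data look safest. The table holds when counts are high. Both cannot be followed.

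**Event.** The prose and the prior refer to the DLT rate, whereas the formula and the table header refer to the SAE rate. The protocol defines these differently, so one patient can count under one label and not under the other.

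This is the plan's only pre-specified numerical toxicity boundary for phase II. Whoever applies or audits it needs one direction and one event to count.

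**Working it through.** **Inputs, all from section 14.2.3.3:** prior Beta(0.5, 0.5); reference rate 30%; cut-off 0.7; the printed boundaries (≥2 at n = 3–5, 3 at 6–7, 4 at 8–10, 5 at 11–13, 6 at 14–16, 7 at 17–19, 8 at 20–22, 9 at 23–26, 10 at 27–29, 11 at 30); and the four printed early-stop probabilities. The phase II total of 30 is in section 14.0.

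**1. Posterior.** With x events in n patients, Pr(rate > 0.30 | x, n) = 1 − F(0.30; 0.5 + x, 0.5 + n − x), where F is the Beta distribution function.

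| Data | Posterior | Sentence (hold if ≤ 0.7) | Table |
|---|---|---|---|
| 0/3 | 0.1269 | hold | continue |
| 1/3 | 0.5843 | hold | continue |
| 2/3 | 0.9111 | continue | hold |
| 3/3 | 0.9951 | continue | hold |
| 10/30 | 0.6628 | hold | continue |
| 11/30 | 0.7900 | continue | hold |

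**2. Which rule made the table.** For each n from 3 to 30, the smallest x with posterior > 0.7 equals the printed boundary, 28 times out of 28. The lowest posterior on the boundary is 0.7032 (at 2/5 and 9/26). The highest posterior one event below it is 0.6993 (8/23). Only a cut-off between these two values reproduces the table, so 0.7 is confirmed.

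**3. Extent of the contradiction.** The possible pairs number the sum of (n + 1) over n = 3 to 30, which is 4 + 5 + … + 31 = 496 − 6 = 490. At every pair the posterior is ≤ 0.7 exactly when x is below the printed boundary. Sentence and table therefore disagree at 490 of 490.

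**4. Which sign is wrong.** Reversing the inner sign instead gives Pr(rate ≤ 30%) ≤ 0.7, equivalent to Pr(rate > 30%) ≥ 0.3. That matches 0 of 28 rows. Only changing the outer sign restores agreement.

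**5. Hold probabilities.** Let f_n(x) be the probability of x events in n patients with no hold so far. Then f_n(x) = (1 − p)·f_{n−1}(x) + p·f_{n−1}(x − 1), with f_0(0) = 1. After each patient from n = 3, the mass in the hold region is removed and added up.

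| True rate | 10% | 20% | 30% | 40% |
|---|---|---|---|---|
| Printed | 0.0885 | 0.3332 | 0.6727 | 0.9128 |
| Table, recomputed | 0.0885 | 0.3332 | 0.6727 | 0.9128 |
| Literal sentence, from n = 3 | 1.0000 | 0.9971 | 0.9570 | 0.8242 |
| Literal sentence, from n = 1 | 1.0000 | 0.9978 | 0.9677 | 0.8671 |

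A hand check of the first look at n = 3: the literal sentence holds at 0 or 1 event. At 10% this has probability 0.9³ + 3(0.1)(0.9²) = 0.729 + 0.243 = 0.972. At 40% it is 0.6³ + 3(0.4)(0.6²) = 0.216 + 0.432 = 0.648. The literal rule holds less often as toxicity rises.

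**6. The event.** The two definitions, side by side:

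- *Acute DLT (section 8.1):* a listed event at least possibly related to treatment, occurring "any time from the initial dose of duvelisib in combination with nivolumab through day 28 of treatment".
- *SAE (sections 8.2.1 and 8.2.2):* defined by seriousness, with no relatedness condition, and collected to 100 days after the last dose.

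The window matters on the plan's own figures. Sections 11.1 to 11.4 give median onset with duvelisib of 3 months for infection, 4 for diarrhea or colitis, 3 for cutaneous reactions and 4 for pneumonitis, all well past day 28.

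The documents give no expected DLT or SAE rate for the combination. As an assumption, take a DLT rate of 20% and an SAE rate anywhere from 10% to 40%. The printed row then gives a hold probability of 0.3332 if DLTs are counted, and 0.0885 to 0.9128 if SAEs are counted.

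**The case against.** The direction fault rests on one symbol read from a PDF by a program, and a misread cannot be excluded. However, the ≥ in the table header of the same section came through correctly, so a misread is possible but not shown. The event mismatch does not depend on that symbol.

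The intended direction is also plain. The section title, the ≥ header and the rising stopping probabilities all point the same way, section 3.2.2 foresees action when the adverse event rate is too high, and the futility rule in section 14.2.2 has its sign the right way round. Staff would use the count table, and nobody would hold at 0/3 and continue at 3/3. The action is a recruitment hold followed by a committee decision, and section 10.1 lets the DSMB and DSMC suspend accrual on their own authority. All this stands and limits the practical risk. It does not make the operative sentence correct.

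On the event, SAE may be loose shorthand for severe adverse event, since section 14.2.3.3 describes DLTs broadly as grade 3 and 4 toxicity and the Protocol Summary uses the word severe. The DLT reading is the dominant one. But the abbreviation list and section 8.2.1 define SAE as serious, so the label still points to a different event. Nor is the bias in one known direction: some DLTs in section 8.1 need not be serious, so the SAE rate could lie below the DLT rate. The assumed range above therefore extends to both sides.

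**Conclusion.** Both faults hold. As supplied, the hold sentence is the exact complement of its table over the whole range the table covers (n = 3 to 30). The table, prior, cut-off and printed probabilities agree with one another, so the error lies in the outer inequality of the sentence, subject to checking the source PDF. The literal hold probabilities of 1.000/0.997/0.957/0.824 (first look at n = 3) show the contradiction and are not a forecast of how the trial would be run.

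The event mismatch is real, but its size cannot be fixed from the documents; the 0.0885 to 0.9128 span rests on the assumed SAE range. The numerical boundary itself does not depend on which event is chosen. The practical risk is limited, but a safety rule should be correct and auditable as written, so the text must be corrected.

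**What to change.** - Check the sign against the source PDF. If it reads as supplied, change ≤ 0.7 to > 0.7 in section 14.2.3.3. Leave the prior, cut-off, boundary table and printed probabilities as they are.
- Reconcile the Protocol Summary and sections 3.2.2, 8.1 and 14.2.3.3 to one monitored event and one observation window, both chosen by the sponsor. Use that term in the formula and the table header.
- As a clarification rather than a correction, state whether the 6 patients carried over from phase I count in this rule. Section 14.0 places them inside the phase II total of 30, and section 14.2.3.3 is silent. Label the printed probabilities as applying to 30 patients monitored from zero.

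The cost is amendment wording only: one symbol, one consistent event term and window, and one sentence on the carried-over patients. No patients are added and no boundary changes.

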14.1. Phase I Portion of the Study

14.1.1. Study Design

The primary objectives of the phase I portion are to determine the maximum tolerated dose (MTD) of duvelisib when combined with anti-PD1 therapy nivolumab, and to decide on its recommended phase II dose (RP2D). Dose escalation will follow the decision rule in the following table, using the three dose levels defined in Section 7.5 (i.e., 15mg Daily, 25mg Daily, and 25mg BID), starting from the lowest dose. The MTD is defined to be the highest dose level at which no more than 1 of 6 treated patients experiences a DLT (DLT is defined in Section 8.1). Cohorts of three to six patients each will be treated at a dose level. Patients should have taken 75% of pills to be included in analysis of their respective cohort, as assessed through pill counts and pill diary. Only toxicities observed during the first treatment cycle will affect dose escalation. Late toxicities observed will be discussed at monthly data safety monitoring boards to determine if dose adjustments should be made.

After MTD is determined, we will decide on RP2D based on an overall consideration of DLT data, as well as immune cell profiling with laboratory correlates. For this purpose, our decision rule in the following table is a slight modification of the standard “3+3” to make sure 6 patients will be accrued at each safe dose in order to have enough patients for laboratory evaluations. RP2D should not be higher than MTD. If the MTD is not reached, RP2D will be decided based on safety data from acute and late toxicities as well as immune cell profiling data by the investigators (see section 13.1).

DECISION RULES FOR DOSE LEVEL ESCALATION

No. of patients with DLT's at this dose level	No. of patients treated at this dose level	Action
≤1	3	Treat 3 more patients at this dose level.
≤1	6	Treat 3 patients at the next higher dose level (or if at the highest level, stop the trial, and declare the dose at this level to be the MTD).

>1	3 or 6	Stop dose escalation. The previous dose is defined as MTD.
----	--------	--

Cohorts need not be completed if clear decisions can be made on the basis of an incomplete cohort. For example, if the first two patients in an intended cohort of three experience DLT's, escalation can be stopped without accruing the third member of the cohort.

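### The phase II toxicity boundary is labelled as a count of SAEs, but its values and stopping probabilities hold only if each patient counts once, and the plan does not say so

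*Combined protocol and SAP*

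**What the plan says.** Section 14.2.3.3 of the combined protocol and SAP says that the study will "continuously monitor the dose limiting toxicity rate of the study combination at 30" per cent, and that "a non-informative prior of Beta (0.5, 0.5) for the DLT rate will be used". The rule begins "We will hold patient recruitment if the posterior probability" and uses a cut-off of 0.7. After a hold, the study committee and the principal investigator decide whether to modify or discontinue the study.

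The boundary table has two columns, "Number of SAEs" (at or above) and "in Number of Patients". It runs from 2 in 3–5 patients to 11 in 30. Below it the plan says "We simulate the operating characteristics under various assumed true toxicity rates" and prints early-stop probabilities of 0.0885, 0.3332, 0.6727 and 0.9128 at true rates of 0.1, 0.2, 0.3 and 0.4.

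Two other places state the patient as the unit. The phase I escalation table in 14.1.1 counts "No. of patients with DLT's at this dose level". The safety tabulation in 14.2.3.4 says "The maximum grade of toxicity for each category of interest will be recorded for each patient".

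**The concern.** The table puts events over patients. A Beta prior on a rate with a binomial likelihood needs a numerator of patients with the event, which cannot exceed the number treated. A count of SAEs has no such limit. One patient can have colitis and a liver enzyme rise, or two admissions, and section 8.2.2 collects SAEs from first dose until 100 days after the last dose.

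Nothing in 14.2.3.3 says how to handle a second event in the same patient. The maximum-grade sentence in 14.2.3.4 does not fill the gap: it governs tabulation, and it works per category, so a patient can still appear more than once.

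At stake is whether the people who apply the rule use the one that was simulated. Under section 10.1, study data are reviewed at meetings that include coordinators, data managers and clinic staff. If they count SAEs as the header says, the printed operating characteristics no longer describe what is done.

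**Working it through.** **Inputs from 14.2.3.3:** prior Beta(0.5, 0.5); threshold rate 0.30; cut-off 0.7; the printed boundary for n = 3 to 30; the four printed early-stop probabilities. The phase II total of 30 patients is from 14.0.

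**Step 1: reproduce the boundary.** For each n, take the smallest x with Pr(p > 0.30 | Beta(0.5 + x, 0.5 + n − x)) > 0.7, where x is the number of patients with the event. All 28 printed values agree. Examples:
- n = 3: x = 2 gives 0.911 and x = 1 gives 0.584, so the boundary is 2.
- n = 5: x = 2 gives 0.703 and x = 1 gives 0.337, so the boundary is 2.
- n = 23: x = 9 gives 0.831 and x = 8 gives 0.699, so the boundary is 9.

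**Step 2: reproduce the operating characteristics.** An exact forward recursion with one Bernoulli(p) outcome per patient and a look after every patient from 3 to 30 gives 0.0885, 0.3332, 0.6727 and 0.9128. These equal the printed values to four decimals, so the table was built on patients with an event.

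**Step 3: apply the header literally.** Suppose one patient has two SAEs and nobody else has any. The event count is 2, which meets the boundary at n = 3, 4 or 5. Counted per patient it is 1 of 3, 1 of 4 or 1 of 5, with posteriors 0.584, 0.447 and 0.337. None exceeds 0.7, so the design calls for no hold.

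**Step 4: illustrate the size.** The documents give no repeat-event frequency. Assume that a fraction f of affected patients has exactly two events, both counted when that patient is counted. Each patient then contributes 0, 1 or 2 events with probabilities 1 − p, p(1 − f) and pf. The recursion of step 2 with the printed boundary gives these hold probabilities:

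| f | p = 0.1 | p = 0.2 | p = 0.3 | p = 0.4 |
|---|---|---|---|---|
| 0 (as printed) | 0.089 | 0.333 | 0.673 | 0.913 |
| 2% | 0.098 | 0.352 | 0.691 | 0.920 |
| 5% | 0.112 | 0.380 | 0.717 | 0.930 |
| 10% | 0.135 | 0.424 | 0.756 | 0.944 |
| 25% | 0.204 | 0.544 | 0.845 | 0.972 |
| 50% | 0.315 | 0.700 | 0.929 | 0.991 |

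**Step 5: relax the timing.** If the second event arrives after further patients have enrolled, it meets a larger denominator and often a higher boundary. Simulation at p = 0.2 with f = 10%, 25% and 50% gives about 0.39, 0.47 and 0.60 for a delay of three enrolments, and 0.37, 0.42 and 0.51 for a delay of six. Both delays are assumptions.

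**The case against.** The strongest reply is that the header is shorthand and a careful reader would take it as patients. Much supports this. The text of 14.2.3.3 speaks of a rate, puts a Beta prior on it and simulates a probability of toxicity, all per-patient quantities. The plan uses event nouns this way elsewhere. The futility table in 14.2.2 heads its column with responses, and the text below treats them as patients who respond. Section 8.1 sets its goal of at most 33% as a percentage of DLTs, for a phase I rule that counts patients. The exact reproduction in steps 1 and 2 points the same way. I accept this as the likely intent.

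The consequence is also limited. Counting events can only bring a hold forward; it cannot miss one that the patient-level rule would trigger on the same type of event. A hold goes to a committee, which would see that two events came from one patient.

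What remains is that the operative table prints a different unit from the model and no sentence corrects it. The phase I table shows that the plan can name the patient as the unit when it chooses to.

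**Conclusion.** The counting unit in the boundary table is mislabelled, and the plan has no rule for repeat events. Severity is minor.

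A reader might infer that the boundary or the simulation is wrong, or that the plan deliberately monitors events. The documents do not support either: every printed number is correct for one outcome per patient.

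A reader might also infer that recruitment will be held well above the stated rates. That is not established. It requires literal use of the header, a repeat-event fraction that the documents do not give, and second events that arrive close to the first. At a true 20% rate the excess over 0.333 ranges from about 2 points (f = 2%) to 37 points (f = 50%) with simultaneous events, and shrinks when the second event is delayed. What does not depend on f is step 3: under the literal header, a single early patient with two events triggers a hold that the design does not call for.

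**What to change.** In 14.2.3.3, relabel the first column *Number of patients with at least one qualifying event ≥*, and add one sentence that defines the monitored rate as the proportion of patients with at least one such event, each patient counting once. The boundary and operating-characteristics tables stand unchanged. Repeat events remain visible in the adverse event tables and in safety review.

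Make this edit together with two separate corrections in the same section. The monitored event is called a DLT in the text but an SAE in the rule and the table, and sections 8.1 and 8.2.1 define these differently. The inequality is printed as ≤ 0.7, whereas the table follows from > 0.7. Replacing SAEs with DLTs in the header would not by itself settle the counting unit. The cost is one header and one sentence, with no new data and no recalculation.
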